#### 7.3.3 Sensitivity Analyses

When subjects' compliance to the protocol are poor and would affect the validity of the efficacy measurements, sensitivity analyses will be conducted on selected efficacy endpoints by excluding those subjects (i.e., using the per protocol analysis set).

For HbA1c change from baseline by visit, similar analyses of those performed using the full analysis set will be performed using the per protocol analysis set. Both t-test and ANCOVA analyses will be repeated using the LOCF algorithm for all visits. Additionally, the pattern of HbA1c over time and change from baseline over time will be evaluated descriptively using summary statistics at each scheduled visit during the entire duration of the study, excluding post-rescue measurements.

Other efficacy endpoints to be used in sensitivity analyses include FPG change from baseline over time, body weight change from baseline over time, systolic and diastolic blood pressure change from baseline over time, and proportion of subjects achieving HbA1c < 7% response

Final – 22November2011 CONFIDENTIAL Page 24 of 30

level over time. The analysis of each of the endpoint will follow the same process described above for HbA1c. All analyses will be performed on the per protocol analysis set.

### 8 Exposure and Compliance

### 8.1 Extent of Exposure to Study Drug

Descriptive summary statistics including the number of subjects, mean, standard deviation, median, minimum, and maximum for the duration of study drug exposure will be presented by treatment group. The duration of study drug exposure is defined as the number of weeks between the date of the first dose and the date of the last dose plus 1 day (that is, exposure in weeks =  $\left[\text{date of last dose - date of first dose} + 1 \text{ day}\right] / 7$ .)

The number and percent of subject who receive at least one dose of double-blind study medication, and the number and percent who complete at least 2, 6, 12, 18, 24, 36, 48, 60, 72, 84, and 96 weeks of treatment will be tabulated.

A by-subject listing of study drug administration will also be presented.

### 8.2 Subject Compliance

Subjects will be given the investigational double-blind drug beginning at Day 1 (Week 0) through Week 96. Investigational product accountability will be done at each study visit after the Week 0 visit through the end-of-treatment visit. Subjects will be instructed to return all unused investigational product at the Week 96 visit in order to perform drug accountability and determine compliance.

The number of administered capsules will be calculated as the number dispensed minus (the number returned plus the number reported as lost/missing and not taken). Treatment compliance will be calculated as total number of administered capsules divided by total number of capsules which should have been taken based on the last completed visit during active treatment period. Treatment compliance will be summarized for all subjects. Summary statistics for treatment compliance percentages, as well as the number and percentage of subjects who are <80%, and ≥80% compliant will be reported for the safety analysis set. Individual subject compliance information will be listed also.

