5.2 Treatments Administered

Study drug will be provided to the pharmacist in bottles of 45 tablets per bottle. Individual bottles of placebo will be provided for the run-in portion of the study. For the first 24 weeks of the study, subject kits will be provided and each kit will contain 4 bottles containing 45 tablets per bottle. For study weeks 25 - 96, subject kits will contain 2 bottles of 45 tablets. Study drug, EGT0001442 10, 15, or 20 mg tablets or matching placebo, will be dispensed by the pharmacy or designated study staff every 6 - 12 weeks. There will be no intra-subject dose escalation or back-titration.

Subjects who require rescue medication due to hyperglycemia will receive standard care for treating type 2 diabetes in addition to the study drug. The pharmacist will dispense the medications per investigator's prescription.

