5.3 Selection and Timing of Dose for Each Patient

Dosing with either active drug or placebo will be based on randomized assignment. All study subjects will be instructed to self-administer one capsule prior to breakfast once daily and complete the dosing log. Subjects will be advised to take the study medication with a glass of water. The tablets will be swallowed without chewing.

On the day of scheduled clinic visits, subjects must fast for a minimum of 10 h prior to the visits at which blood samples will be drawn. During fasting, only water will be permitted. Subjects will be asked to record the meals they consume and the time that they last ate prior to blood draw for FPG and other laboratory testing.

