5.9 Packaging and Labeling

5.9.1 Study drug for main treatment period

EGT0001442 tablets and placebo are packaged in high density polyethylene (HDPE) bottles sealed with a child resistant closure. Each kit will include 4 bottles of study drug. The product is packaged with 45 tablets per bottle including a 3 tablet overage in each bottle for accidental loss of study drug during the treatment period between visits.

Study drug bottles will be labeled with the protocol number, product identification, lot number, kit number, Sponsor's name and address, and the investigational drug caution statement.

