  - V8-V15 and ET: CBC, electrolytes, BUN, creatinine, Lipids (TG, TC, HDL-c), ALT, AST, bilirubin (total and direct), HbA1c, FPG. PT only at V8, and V15 or ET.
-  Clean catch sample to be collected at each visit and sent to the central lab. Urine drug screen on screening (visit 1). On-site urine dipstick to be performed at all visits except V2.
- NMP22 testing will be performed at screening (V1), randomization (V3), and at weeks 24 (V8), 48 (V10), 72 (V12), and 96 (V14) or when clinically indicated. For subjects who do not have baseline NMP22 testing following Protocol Amendment 1 (11 April, 2011), NMP22 testing will be performed in the next visit or within 4 weeks after Amendment is approved, whichever comes first.
- Adverse events of special interest are specified to be:
  - Cardio- and cerebro- vascular events,
  - Genitourinary infections
  - Increase in creatinine from baseline by 0.5 mg/dL or more
  - Increase in ALT, AST or bilirubin to >3x ULN
- Visit to be conducted one week after last dose of study drug whether subject early terminates from study or completes V14.

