#### **5.1 Protocol Deviations**

Subject compliance to the protocol will be evaluated prior to unblinding the study and subjects with major protocol deviations will be identified. Specific criteria for what constitutes a major protocol deviation will be determined by the study team. The following criteria will be considered:

- Failure to meet key inclusion/exclusion criteria
- Use of prohibited concomitant medications
- Noncompliance with the study medication dosing schedule

Protocol deviations will be tracked by the clinical team using TrialWatch on an on-going basis and will be listed by subject. A table summary by treatment group and listing of major protocol deviations will be presented by subject for all randomized subjects.

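### The SAP 8.2 compliance ratio counts supply issued at the last completed visit but ends the expected count there, overstating compliance for subjects lost with that supply unaccounted for

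*SAP*

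**What the plan says.** SAP 8.2 defines treatment compliance as a ratio. The numerator, capsules administered, is "calculated as the number dispensed minus (the number returned plus the number reported as lost/missing and not taken"). It covers all supply issued and has no end date. That total is then "divided by total number of capsules which should have been taken based on the last completed visit during active treatment period". Table 14.1-4.2 shows summary statistics of the percentages by arm, and "the number and percentage of subjects who are <80%, and ≥80% compliant will be reported for the safety analysis set". Section 8.2 has no rule for capsules that are neither returned nor reported lost, no rule for an expected count of zero, and no cap at 100%.

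The same section schedules accountability at each visit after Week 0 through end of treatment, and asks for unused product back at Week 96. SAP Table 1 has double-blind drug issued at Weeks 0, 6, 12, 18, 24, 36, 48, 60, 72 and 84, and none at Week 2 or Week 96.

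On supply sizes, Protocol 5.9.1 says "The product is packaged with 45 tablets per bottle including a 3 tablet overage in each bottle", and Protocol 5.2 says "For study weeks 25 - 96, subject kits will contain 2 bottles of 45 tablets". Dosing is one unit a day: Protocol 5.3 has subjects "self-administer one capsule prior to breakfast once daily".

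**The concern.** A compliance ratio is interpretable only if both terms cover the same days. Here most visits that close one dosing interval also hand out the supply for the next. If the subject is never seen again and that supply is never accounted for, it enters the numerator in full and adds nothing to the denominator.

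The error always raises the score. It does not arise for a subject who completes and returns the remainder at Week 96, because nothing is issued at that visit. It falls on subjects who are lost, for whom low adherence is a natural question. At stake is the accuracy of the compliance percentages and of the share at or above 80% in Table 14.1-4.2, and their comparability between arms if loss to follow-up differs by arm.

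**Working it through.** **The plan's own figure.** The SAP gives no worked compliance value. The bottle size can be reproduced: 6 weeks × 7 days × 1 per day + 3 overage = 45. Two bottles hold 90 = 12 × 7 + 6.

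**Formula.** Let *w* be the week of the last completed visit, *E* = 7*w* the expected count, *t* the capsules truly taken by then, and *L* the units issued at that visit and never accounted for. Earlier leftovers are taken as returned.

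- Score under SAP 8.2 = (*t* + *L*)/*E*
- True adherence to that visit = *t*/*E*
- Inflation = *L*/*E*
- Lowest true adherence scored at 80% or more = max(0, 0.8*E* − *L*)/*E*

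**Results**, with one 45-unit bottle issued at Weeks 6 to 18, 90 units from Week 24, and none of the last issue taken:

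| Lost after week | *E* | *L* | Inflation (points) | True adherence that scores 80% |
|---|---|---|---|---|
| 6 | 42 | 45 | 107.1 | 0% (33.6 − 45 is negative) |
| 12 | 84 | 45 | 53.6 | (67.2 − 45)/84 = 26.4% |
| 18 | 126 | 45 | 35.7 | (100.8 − 45)/126 = 44.3% |
| 24 | 168 | 90 | 53.6 | (134.4 − 90)/168 = 26.4% |
| 36 | 252 | 90 | 35.7 | (201.6 − 90)/252 = 44.3% |
| 48 | 336 | 90 | 26.8 | (268.8 − 90)/336 = 53.2% |
| 60 | 420 | 90 | 21.4 | (336 − 90)/420 = 58.6% |
| 72 | 504 | 90 | 17.9 | (403.2 − 90)/504 = 62.1% |
| 84 | 588 | 90 | 15.3 | (470.4 − 90)/588 = 64.7% |

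**Example.** By Week 12 a subject has taken 42 of 84, returned 48 of the first 90, received 45 more, and is then lost. As written: (135 − 48)/84 = 103.6%, scored as compliant. With supply issued at Week 12 left out: (90 − 48)/84 = 50.0%.

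**The same 50% taker at other times.** The score is 157.1% after Week 6, 85.7% after Week 18 or 36, 76.8% after Week 48 and 65.3% after Week 84. The last two are inflated but still fall below 80%.

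**Very early loss.** After Week 2, with the Week 0 bottle never returned, the score is 45/14 = 321% whatever was taken. Before any post-baseline visit *E* = 0 and the ratio is undefined.

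**Size of the first issue.** Protocol 3.1 gives 6 weeks of drug at randomization; SAP 3.1 gives 24 weeks. If four bottles (4 × 45 = 180) go out at Week 0 and each finished bottle is handed back, 135 units are outstanding after Week 6 and 90 after Week 12. Inflation is then 135/42 = 321.4 and 90/84 = 107.1 points, and any intake scores 80% at either visit.

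**Withdrawn subjects who return their supply.** Take the Week 12 subject again, now taking 10 more capsules and returning the other 35. With the denominator held at Week 12 the score is 52/84 = 61.9%, correctly below 80%. If an end-of-treatment visit 28 days later counts as the last completed visit, it is 52/112 = 46.4%. A fully adherent subject who takes 10 more capsules, with the denominator held at Week 12, scores 94/84 = 111.9%.

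**Effect on the table.** With 150 subjects in an arm, each misclassified subject moves the share at or above 80% by 1/150 = 0.7 points.

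**The case against.** The strongest reply is that the plan already provides for subjects who stop early. Protocol 5.11 requires all product to be returned at the end of treatment. The footnote to SAP Table 2 refers to an end-of-treatment visit for subjects who withdraw early, separate from the one-week follow-up, and SAP 8.2 runs accountability through end of treatment. If that visit is the last completed visit, both terms end together. A subject who stops on Day 35 having taken 20 of 35 then scores 20/35 = 57%, not the 20/14 = 143% obtained by holding the denominator at Week 2.

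This stands for withdrawn subjects who attend. A reader might infer that withdrawn subjects in general are scored as compliant; the documents do not support that. Some ambiguity remains, because SAP Table 1 has no column for an early end-of-treatment visit and its footnote provides only for follow-up: "Visit to be conducted one week after last dose of study drug whether subject early terminates from study or completes V14". At most this leaves the smaller mismatch shown above. The reply does not help with subjects who are lost and return nothing.

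A second reply is that the effect is confined to one descriptive table without p-values, whose minimum and maximum would expose values far above 100%. That is right about reach. But a visible maximum does not correct the mean or the count at or above 80%, and a value inflated from 50% to 85.7% would not stand out.

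A third is that the bottle counts describe tablets in the protocol dated 02 February 2011, whereas the SAP describes capsules and its table shells cite later protocol versions. That also stands: the percentages are conditional on those counts. The mismatch in the formula is not.

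**Conclusion.** SAP 8.2 is wrong as written for a definable group: subjects lost to follow-up whose last issue is neither returned nor reported lost. Their compliance is always overstated. The overstatement is severe for early loss and moderate later, when a subject needs true adherence of about 53% to 65% to reach the 80% line. So it would be too strong to say that lost subjects generally score as compliant on few capsules. Those lost before any post-baseline visit get an undefined value, not a compliant one.

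The figures assume that the protocol's bottle counts carry over to capsules and that none of the last issue was taken. A larger first issue would increase the early inflation.

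Two further inferences go beyond the documents. The first is that the per-protocol set is distorted. SAP 5.1 lists "Noncompliance with the study medication dosing schedule" only as a criterion to be considered, leaves the specifics to the study team, and ties neither this ratio nor the 80% cut to that set. The set is affected only if the team chooses to use the ratio. The second is that 17 of 150 subjects per arm (150 enrolled less 133 evaluable, SAP 3.5) measures how many are affected. That is a sample-size allowance; the number with an unaccounted last issue is unknown.

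The primary analysis uses the full analysis set and does not depend on compliance. Severity: minor.

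**What to change.** Use one period for both terms in SAP 8.2.

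- Where the final supply is accounted for: count dispensed minus returned minus lost, against the days from first to last dose as in the exposure definition of SAP 8.1, at one capsule per day.
- Where it is not: end both terms at the last visit with accountability, use the count made at that visit, and leave out supply issued at it.
- Where no accountability visit exists: report compliance as not evaluable and show the number of such subjects in Table 14.1-4.2.
- Add a lost/missing count to Listing 16.2-6.1. It currently shows capsules dispensed and returned only, although the SAP 8.2 numerator needs the lost count.
- If the study team uses compliance for the dosing criterion in SAP 5.1, apply the same definition there.

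The cost is a few sentences, a small programming change, and a few subjects without a compliance value. The second rule needs counts recorded by visit. SAP 8.2 plans them, but Protocol 5.8 describes accountability as recorded at the end of treatment, so confirm that the case report form captures them. The size of the first issue should also be reconciled between Protocol 3.1 and SAP 3.1 before programming.

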## 9 Safety

All safety summaries and analyses will be performed using the safety analysis set.

Final – 22November2011 CONFIDENTIAL Page 25 of 30

#### 9.1 Adverse Events

### 9.1.1 All and Treatment Emergent AEs

All AEs will be coded using MedDRA version 14.0. A treatment-emergent adverse event (TEAE) is one with a start date on or after the date of the first administration of study drug. Only TEAEs will be included in summary tables. All AEs will be included in listings.

Partial start dates of AE will be assumed to be the earliest possible date consistent with the partial date. In the case of a missing year, the year will be assumed to be the year part of informed consent date of that subject. In the case of a completely missing start date, the start date will be assumed to be prior to date of the first administration of study drug.

In general, AEs will be presented in descending order from the system organ class (SOC) with the highest total incidence (that is, summed across all treatment groups) for any adverse event within the class to the SOC with the lowest total incidence. Within the SOC level, AEs will be presented in descending order from the MedDRA preferred term (PT) with the highest total incidence to the PT with the lowest total incidence. If the total incidence for any two or more PTs within an SOC is equal, the PTs will be presented in alphabetical order. A PT will not be presented if no adverse events occur within the level. At each SOC and PT level of summarization, a subject will be counted once if he/she reports 1 or more events at that level.

A summary of the number and percentage of subjects with TEAEs by severity (mild, moderate, and severe) will be produced. Subjects who experience the same event several times, with different severity will only be counted once according to the maximum severity experienced at each level of summarization. AEs with missing severity will be considered to be severe for the purposes of summarization.

TEAEs will also be summarized in a table by relationship to study drug (related versus not related to study drug). Events reported as not related or unlikely will be categorized as not related; events reported as possible, probable, definite, unknown will be categorized as related. If a relationship to the study drug is missing or unknown, it will be assumed, for the purpose of analyses, to be treatment-related.

A summary of most common TEAEs, defined as any AE on the preferred term level that has an incidence rate >5% among the subjects in either treatment groups, will be produced by treatment.

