9.6.1 Adverse Events

Adverse events will be mapped to preferred term and body system using the Medical Dictionary for Regulatory Activities (MedDRA) dictionary. The number and percentage of patients reporting adverse events will be determined by relationship to treatment and by severity of the event. Drug-related adverse events will be considered those to be at least possibly related to EGT0001442 administration.

Adverse event listings will be provided for the following subsets:

- All treatment emergent AEs (TEAEs)
- All TEAEs at least possibly related to EGT0001442
- Serious TEAEs (if any)
- TEAEs leading to study discontinuation (if any)

AEs are treatment emergent if occurring on or after EGT0001442 administration. TEAEs will be considered at least possibly related to EGT0001442 based on the investigators assessment. Only TEAEs will be tabulated in summary tables.

Tabulations will display TEAEs by severity, and relationship to EGT0001442.

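### SAP 9.1.1 dates undated adverse events, and some partly dated ones, before first dose, so they drop out of the TEAE tables

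*SAP*

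**What the plan says.** SAP 9.1.1 defines emergence by date: "A treatment-emergent adverse event (TEAE) is one with a start date on or after the date of the first administration of study drug". It then limits tabulation: "Only TEAEs will be included in summary tables". Listings are not limited: "All AEs will be included in listings".

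Three rules cover incomplete start dates:

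- Partial date: "Partial start dates of AE will be assumed to be the earliest possible date consistent with the partial date".
- Year missing: "the year will be assumed to be the year part of informed consent date of that subject".
- No date at all: "the start date will be assumed to be prior to date of the first administration of study drug".

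Nothing in the section uses the stop date, the visit of report, the action taken or the causality rating to keep such an event as a TEAE. No other part of either document overrides the rules.

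The same section handles other missing fields differently. On severity it says "AEs with missing severity will be considered to be severe for the purposes of summarization". A missing or unknown relationship is taken as related.

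Protocol 9.6.1 defines emergence by when the event happens ("AEs are treatment emergent if occurring on or after EGT0001442 administration") and has no imputation rule.

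**The concern.** All three date rules can only move an event earlier. For an event that truly began on treatment, the sole possible misclassification is from emergent to not emergent. The severity and relationship rules go the other way and assume the worse case. Together they can give an odd result: an event with neither date nor relationship recorded is assumed to be caused by the drug and also to have begun before it.

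The wording closely follows the medication rules in SAP 6.4. There an early start date does little harm, because a drug that continues past first dose still counts as concomitant and a fully missing stop date means ongoing. Adverse events have no such safeguard.

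The outputs at stake are the TEAE tables: overall, by severity, by relationship, most common, serious, leading to discontinuation, and hypoglycemia. For some events of special interest these tables matter more than usual. Protocol 9.6.2.1 and 9.6.2.4 promise summaries of genitourinary infections and of renal and urinary disorders, whereas SAP 9.1.3 gives those categories by-subject listings only. Their main comparison by arm is therefore the preferred-term TEAE tables.

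**Working it through.** The plan states no figure to reproduce. The check is what the rules do to an event that truly began on treatment.

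**Inputs from the documents.** The rules above. Treatment lasts 96 weeks, or 672 days (SAP 3.1); the main period is 24 weeks, or 168 days. Screening lasts up to 21 days and run-in is nominally 14 days (Protocol 7), so consent precedes first dose by about 14 to 35 days.

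**Assumptions not in the documents.** Onset is equally likely on each on-treatment day. First dose is equally likely on each of the 365 days of 2011.

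**Step 1. Worked cases** (first dose 15 Sep 2011, consent in 2011)

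| Recorded start | Imputed start | Class |
|---|---|---|
| Nothing | before first dose | not TEAE |
| Sep 2011 (true 20 Sep) | 1 Sep 2011 | not TEAE |
| 2011 (true 10 Nov) | 1 Jan 2011 | not TEAE |
| 10 Mar, no year (true 2012) | 10 Mar 2011 | not TEAE |
| Jun 2012 | 1 Jun 2012 | TEAE |
| 2012 | 1 Jan 2012 | TEAE |

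**Step 2. Share of on-treatment events misclassified**

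*No date:* 100%, directly from the rule.

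*Day missing.* Only onsets in the month of first dose are affected, and none if first dose is on the 1st. A month of L days gives L(L−1)/2 affected onset days over its possible first-dose days. For 2011: (7×465 + 4×435 + 378)/365 = 5,373/365 = 14.72 days on average. 14.72/672 = 2.2%; 14.72/168 = 8.8%.

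*Only the year known.* Only onsets in the calendar year of first dose are affected, and none if first dose is on 1 January. The average is 364/2 = 182 days, and 182/672 = 27.1%. Over 24 weeks the count is capped at 168 days: (197×168 + 167×168/2)/(365×168) = 47,124/61,320 = 76.8%.

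*Year missing.* Let first dose fall on day j of 2011. If consent is in the same year, the affected onsets number max(0, j−198) over 168 days, and (j−1) + max(0, j−59) over 672 days. If consent fell in 2010 (j up to 14 for a 14-day lag, up to 35 for a 35-day lag), every onset is affected.

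- 24 weeks: the first term sums to 167×168/2 = 14,028. Adding 14×168 = 2,352 gives 16,380/61,320 = 26.7%. Adding 35×168 = 5,880 gives 19,908/61,320 = 32.5%.
- 96 weeks: 365×364/2 + 306×307/2 = 66,430 + 46,971 = 113,401. Adding 14×672 − 91 = 9,317 gives 122,718/245,280 = 50.0%. Adding 35×672 − 595 = 22,925 gives 136,326/245,280 = 55.6%.

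These sums ignore 29 February 2012; a day-by-day count that includes it gives the same figures to one decimal.

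| Missing | First 24 weeks | 96 weeks |
|---|---|---|
| Whole date | 100% | 100% |
| Year | 27–33% | 50–56% |
| Day and month | 76.8% | 27.1% |
| Day | 8.8% | 2.2% |

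**Step 3. Sensitivity to the recruitment calendar.** The day-missing figures hardly move (2.2%, and 8.6–8.9% over 24 weeks). The middle two rows do move.

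- First doses from 11 April to 22 November 2011: year missing 54.6% over 96 weeks and 21.7% over 24; year only 22.7% and 78.3%.
- First doses all in May 2011: year missing 31.5% and 0%; year only 34.2% and 100%.
- First doses on 15–20 January 2012: year missing over 96 weeks is 2.5% if consent was in the same January and 100% if it was in the previous December.

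**Step 4. Effect on the comparison.** If a fraction m of events is lost in each arm, event rates r₁ and r₀ become (1−m)r₁ and (1−m)r₀. Their difference shrinks to (1−m)(r₁−r₀), and their ratio is unchanged.

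**The case against.** The case for leaving the rule alone has four parts.

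- **Most partial dates are unharmed.** With only the day missing, about 98% of on-treatment events over 96 weeks, and about 91% in the first 24, are still classed as TEAEs. This stands, so the point covers only partial dates whose imputed value precedes first dose.
- **The events stay visible.** The shell for Table 14.3-1.1 has a by-arm row for any AE that is not limited to TEAEs. The listings of deaths, serious events, discontinuations and each special-interest category show all events, and their layout carries a treatment-emergent flag. This stands too, so a reader who infers that affected events survive only in listings goes too far. But the any-AE row is a single count without term, severity or causality, and listings are not a comparison by arm.
- **Incomplete dates may be rare.** Events are elicited at each visit (Protocol 6.9.2), queries are raised and resolved (10.10), and errors are corrected before lock (10.9). Serious events reach the sponsor within 24 hours, and non-serious events leading to discontinuation within 3 working days (6.9.3), so those tables are the least exposed. This limits the likely size but not the direction.
- **The alternative also errs.** It counts some screening or run-in events as emergent. That is true, and it is the same kind of error the section already accepts for severity and relationship.

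Two stronger readings are tempting. A reader might infer that the missing-date rule is wrong for at least 95% of undated events, because AE recording is first scheduled at Visit 3 and 97 of 99–102 weeks follow first dose (97/102 = 95%, 97/99 = 98%). That is a share of time. It becomes a share of events only if undated onsets are spread evenly, which no section supports. Protocol 6.9.1 counts worsening of existing problems as AEs, and undated onsets may cluster there. A reader might also infer a general bias toward no difference between arms. With equal missingness only the absolute difference shrinks, as Step 4 shows, and the documents give no reason to expect unequal missingness. Incidence by subject will usually change less still, because another dated event at the same level keeps the subject in the count.

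**Conclusion.** The point holds for two groups: all events without a start date, and partly dated events imputed to before first dose. The SAP classes them as not treatment emergent whatever else is known about them. That is anti-conservative for safety and inconsistent with the rest of the section.

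The misclassified shares are conditional on the date part being missing; they are not shares of all adverse events. They rest on uniform onset and on first doses spread over 2011, and the figures for a missing year or a year alone shift with the recruitment calendar. The 100% for a fully missing date needs no assumption.

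The documents give no rate of incomplete dates, so the number of events lost cannot be stated and may be small. The efficacy analyses are not affected. The rule should be corrected because it points the wrong way and is cheap to change, not because a large distortion has been shown.

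**What to change.** Replace the start-date rules in SAP 9.1.1 with two sentences to this effect: an adverse event with a missing or partial start date is treatment emergent unless the known parts of that date, or the stop date, show that it began before first dose. Its start is then imputed as the first-dose date or, if the known parts exclude that day, the earliest later date that agrees with them.

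In the worked cases, Sep 2011 and 2011 would both become 15 Sep 2011, and 10 Mar without a year would become 10 Mar 2012 unless the stop date rules that out. If the recorded parts and stop dates are correct, 0% of truly on-treatment events are lost under any pattern of missing parts.

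The cost is two sentences and a small programming change. The downside is that some pre-dose events with incomplete dates will be counted as TEAEs, so the counts may look slightly less favourable.
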